 - o mean peripartum change in haemoglobin and haematocrit as well as haemoglobin drop > 2 g/dL,
 - o transfer to intensive care unit (ICU),
 - o or death from any cause.
- To assess potential adverse effects of TXA:
 - o Hemodynamic parameters,
 - o adverse gastrointestinal events, renal, hepatic, and coagulation function,
 - o and any venous or arterial thrombosis at any time during the woman's postoperative course.

METHODOLOGY

Research design

Open-label parallel randomized control trial.

Target population

Women undergoing caesarean sections at Sally Mugabe and Parirenyatwa Hospitals based on set inclusion and exclusion criteria.

Inclusion criteria

- Estimated gestational age of 37 weeks or more
- Live intrauterine foetus
- Elective or emergency caesarean delivery
- Signed informed consent

Exclusion criteria including any of the following factors or conditions identified prior to surgery

- History of coagulopathies or conditions predisposing them to thromboembolic phenomena,
- seizure history,
- autoimmune disease,
- placental abruption,
- placenta praevia,
- abnormally adherent placentae if identified on prenatal ultrasound,
- eclampsia or HELLP syndrome,
- known hypersensitivity to TXA,
- planned general anaesthesia,
- caesarean delivery for the second twin or second/third triplet(s) after vaginal birth of the first twin,
- poor understanding of English/Shona languages,
- those who have received anticoagulants in the week before delivery
- persons-under-investigation for COVID-19 and confirmed COVID-19 positive women.

Women will receive individual information in late pregnancy about the trial from obstetricians and midwives during antenatal clinic visits or from anaesthetists during the pre-caesarean visit, or both. Women may be pre-included (receive information and sign consent forms) for caesareans both before and during labour when the investigator considers that the woman is likely to have a caesarean delivery. The aim of pre-inclusion is to facilitate recruitment, particularly the recruitment of caesareans during labour, which may be decided upon and performed in emergency situations. Women recruited prior to emergency caesarean delivery (in labour) sign consent to have the caesarean section while in labour. We therefore consider that having received information about the trial during the antenatal period and on the labour ward, they will also be able to provide informed consent for inclusion into the trial at the same time.

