Study Setting

The study will be performed at two tertiary institutions that are affiliated to the University of Zimbabwe that serve as referral centres for clinics located in Harare as well as district and provincial hospitals in the surrounding provinces: Sally Mugabe Central Hospital Maternity Unit and Parirenyatwa Group of Hospitals i.e. Mbuya Nehanda Maternity Hospital (MNMH). Most of these patients understand both English and Shona languages.

Sample size

The sample size has been calculated assuming a proportion of 2.1% PPH in the experimental group and 5.8% (34) in the control group at 95% confidence interval and 90% power using the Fleiss formula giving a minimum sample size of

$$n = \frac{\left[\frac{Z_{\alpha}\sqrt{(r+1)\overline{p}\overline{q}} + Z_{\beta}\sqrt{rp_{1}q_{1} + p_{2}q_{2}}\right]^{2}}{r(p_{1} - p_{2})^{2}}$$

$$n = \frac{\left[\frac{1.96\sqrt{(1+1) \times 0.0395 \times 0.9605} + 1.28\sqrt{0.021 \times 0.979 + 0.058 \times 0.942}\right]^{2}}{(0.021 - 0.058)^{2}}$$

= 581 per group

Thus, total minimum sample size N = 1, 162 women

Where: n = sample size

 Z_{α} = 1.96 at 95% confidence interval

```
\alpha = probability of a type I error (significance level) = 0.05 \beta = probability of a type II error (1 – power of test)
```

 p_1 = proportion of PPH in the experimental group = 0.021

 p_2 = proportion of PPH in the control group = 0.058

r = ratio of control group/population 2 to experimental group/population 1

q = 1-p

Randomization

A randomized allocation to study and control groups using computer-generated random numbers will be prepared by the trial statistician.

Pharmacy Plan

Oxytocin iv is dispensed weekly from the pharmacy to theatre, where it is stored in a refrigerator in the custody of the sister in charge. All patients undergoing caesarean delivery routinely receive 10IU oxytocin iv, administered slowly by the anaesthetist after delivery of baby at Sally Mugabe Hospital Maternity Unit and Mbuya Nehanda Maternity Hospital. Cold chain will be maintained up to the administration of drug to the patient.

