TXA obtained for the study will be kept in theatre. This is to ensure an uninterrupted supply of the drug for the study. The TXA vials will be kept in theatre in a locked drug cupboard accessible to the researcher and research assistants at the authorization of the sister in charge. A dispensing register for the drugs will be kept together with the drugs. Patient details and study number, amount of TXA dispensed and wasted will be entered into the study register for accountability and to guard against abuse.

Intervention

The participants in the intervention arm will receive generally from the anaesthetist or nurse anaesthetist TXA (1g), administered slowly (over 30 – 60seconds) at the time of skin incision. Participants in both the intervention arm and control group will receive the routine prophylactic 10 IU oxytocin intravenously at birth of the baby. All other aspects of management of the caesarean section will be identical in both arms (34).

Other aspects of the caesarean delivery

- The surgical team will decide on the administration of additional uterotonics and the management of PPH, in a manner consistent with local guidelines. In particular, the use of TXA for the treatment of PPH will be allowed and left to the practitioner's discretion according to the hospital protocol.
- Because the surgeon's level of experience may affect estimated blood loss during or after a caesarean delivery, the obstetrician's experience, categorized as senior resident medical officer, senior house officer, junior registrar, senior registrar or consultant will be recorded (34).

Assessment

Data will be collected and recorded on the data collection tool. Any adverse event will to be reported on the IRB adverse event reporting form.

Primary outcome measure

Estimated blood loss (EBL) will be determined using haematocrit, haemoglobin, and visual estimates.

Calculated estimated blood loss = estimated blood volume \times (preoperative haematocrit – postoperative haematocrit) / preoperative haematocrit. Where estimated blood volume (mL) = weight (kg) \times 85).

The calculation is an objective measure to estimate blood loss because of the inaccuracy of other methods used to determine blood loss and caesarean delivery(35).

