Quantitative variables will be expressed, as appropriate, as means with standard deviations (and compared by Student's t-test) or as medians with interquartile ranges (compared by the Wilcoxon rank-sum test). Chi-square or Fisher's exact tests will be used, as appropriate, to compare categorical variables. The effects of TXA will be expressed as relative risks with 95% confidence intervals for categorical outcomes and as mean differences with 95% confidence intervals for quantitative outcomes. The results will also be expressed as absolute risk differences with 95% confidence intervals for binary outcomes.

Two specified subgroup analyses will examine the primary outcome in subgroups of women at high risk of PPH. The subgroups will include women who undergo a caesarean during labour and those who are at risk for PPH according to a composite definition (having at least one risk factor with an odds ratio of 3 or greater in the literature (34) history of any of PPH, hypertensive disorder of pregnancy, multiple pregnancy, or caesarean during labour). Moreover, prespecified subgroup analyses will examine the secondary outcomes in the subgroup of women who undergo a caesarean during labour. We will use the Benjamini–Hochberg procedure to adjust for multiple comparisons of secondary outcomes or subgroups (34). A statistical test may be significant by chance but in reality, not significant. The Benjamini-Hochberg method is used to control for this false discovery rate in statistical tests. Statistical analysis will be conducted using Stata v16. Feasibility

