Prior to the COVID 19 pandemic HMH delivered 1,335 pregnancies while a total of 535 pregnancies per month were delivered at MNMH. On average 60 elective and 250 emergency caesarean sections were done at HMH per month, while 80 elective and 210 caesarean deliveries on average are done at MNMH. Based on a review of the theatre delivery records during the period from April 2020 to August 2020 an average of 154 emergency caesarean sections were done monthly at MNMH, while an average of 149 emergency caesa were done at HMH. During this COVID period an average of 303 caesarean sections are being done per month. About 90% of these meet the inclusion criteria. Assuming a participation rate of 50% of these, an inclusion period of 8 months should make it possible to recruit 1,162 participants. Given that the lockdown conditions are being eased, with staff returning after industrial action, and that the hospitals are slowly reintroducing antenatal clinics, there should be an increase in caesarean sections (elective and emergency) across both institutions which may allow us to reach the targeted number in a shorter time period.

Impact of COVID-19

Coronavirus disease 2019 (COVID-19) has led to the deadliest pandemic observed in over 100 years (40). Healthcare workers and potentially researchers in obstetric wards are at a particularly increased risk for occupational exposure due to long periods of interaction with patients during labour, patient care involving multiple team members, the unpredictable occurrence of sudden obstetrical emergencies with their potential for unanticipated intubations in women undergoing labour and delivery. Presence on an obstetrical ward presents a real risk for infection to the research team (41).

At the point of recruitment, the researcher and team will employ a combination of standard contact and droplet precautions, with further precautions undertaken during aerosol-generating procedures such as recruitment of patients in labour (42).

The standard precautions are used to prevent or minimize transmission at all times. These include hand hygiene, appropriate use of personal protective equipment (PPE), safe handling of sharps, respiratory hygiene, occupational health and injection safety (42).

Transmission-based precautions – droplet or contact include:

hand hygiene which is the most essential aspect

- PPE which consists of gloves, gown, and a medical mask
- Safe waste management (42).

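### No stratification is stated and the primary comparison is crude and pooled, although hospital and labour status could be used; operator grade is recorded but never used. The cost is modest precision, not bias.

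*Combined protocol and SAP*

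**What the plan says.** **Design and allocation.** The trial is an "Open-label parallel randomized control trial" (Research design) at two hospitals: "The study will be performed at two tertiary institutions that are affiliated to the University of Zimbabwe" (Study Setting). The Randomization section consists of one sentence: "A randomized allocation to study and control groups using computer-generated random numbers will be prepared by the trial statistician". It names no stratum, block or minimisation factor, and does not say whether each hospital has its own list.

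**Operator grade.** Under Other aspects of the caesarean delivery the plan gives its reason, "Because the surgeon's level of experience may affect estimated blood loss during or after a caesarean delivery, the obstetrician's experience", and then says that this will be recorded in five grades. Statistical methods and data reporting does not mention the variable.

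**Primary comparison.** "Chi-square or Fisher's exact tests will be used, as appropriate, to compare categorical variables", with relative risks and absolute risk differences and their 95% confidence intervals. No covariate, stratum or by-hospital result is named.

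**Labour status.** The same section puts caesarean during labour in a composite of risk factors said to have a literature odds ratio of 3 or greater, and makes it a subgroup for the primary and secondary outcomes. It plays no part in allocation or in the main estimate.

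**Case mix.** Feasibility reports pre-COVID monthly volumes: "On average 60 elective and 250 emergency caesarean sections were done at HMH per month, while 80 elective and 210 caesarean deliveries" at MNMH.

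**The concern.** A plan that regards a factor as strongly prognostic, and can hold it for every woman, would normally either balance it in the allocation or account for it in the primary estimate. This one does neither for labour status or hospital. A chance imbalance in either would pass unadjusted into the headline relative risk and risk difference. Choosing covariates after such an imbalance is seen, in an open-label trial, invites argument about selective adjustment. With no by-hospital display, a result carried by one hospital would not be apparent. Operator grade is a smaller matter of the same kind: the plan gives a reason to collect it and states no use for it.

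**Working it through.** **1. The plan's own sample size.** The inputs come from the Sample size section: "assuming a proportion of 2.1% PPH in the experimental group and 5.8% (34) in the control group at 95% confidence interval and 90% power", with 1:1 allocation and the two-sided 5% level implied by Z = 1.96. The pooled Fleiss formula is

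n = [1.96√(2 × 0.0395 × 0.9605) + 1.28√(0.021 × 0.979 + 0.058 × 0.942)]² / 0.037² = 579.8 with the rounded Z values, and 581 after rounding up with unrounded ones. The stated 581 per group is reproduced.

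Expected events: 581 × 0.021 + 581 × 0.058 = 12.2 + 33.7, about 46. Standard error of the risk difference: √[(0.021 × 0.979 + 0.058 × 0.942)/581] = 1.14 points.

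**2. Case mix (Feasibility, pre-COVID).** Elective share: HMH 60/310 = 19.4%; MNMH 80/290 = 27.6%, reading the 210 at MNMH as emergencies, which the text does not say. Emergency share overall: 460/600 = 76.7%. Emergency is used below as a proxy for in labour. That is an assumption, as the documents do not equate the two.

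**3. Chance imbalance under simple 1:1 randomisation.** The SD of the between-arm difference in a factor with prevalence q is √(2q(1−q)/581).

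- Labour, q = 0.767: SD 2.48 points, 95% range ±4.9 points.
- Hospital, q = 0.5 (assumed equal split): SD 2.93 points, 95% range ±5.7 points.

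These are imbalances in the covariate, not in PPH, so they must be converted.

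**4. Effect on the risk difference, labour status.** Let a and b be the control risks out of and in labour. Solve 0.767b + 0.233a = control rate, with b/(1−b) = 3a/(1−a). The 95% shift is the ±4.9-point imbalance times (b − a). The share of outcome variance is q(1−q)(b−a)²/[p(1−p)].

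| Control rate p | a | b | 95% shift | Share of outcome variance |
|---|---|---|---|---|
| 5.8% (design) | 2.4% | 6.8% | 0.049 × 4.45 = ±0.2 points | 0.6% |
| 31.4% (pilot, per-protocol) | 15.9% | 36.1% | 0.049 × 20.3 = ±1.0 point | 3.4% |

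The planned effect is 3.7 points. The pilot difference is 31.4 − 22.6 = 8.8 points.

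**5. Effect on the risk difference, hospital.** The documents give no PPH rate by hospital. For assumed control-rate gaps of 2, 4 and 8 points, the 95% shift is ±0.11, ±0.23 and ±0.46 points. This is 0.3%, 1.1% and 4.3% of the variance of the risk difference.

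**6. Simulation (N = 1,162, simple randomisation): crude test against Mantel-Haenszel.** All stratum rates are assumed.

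| Scenario | Power, crude | Power, stratified |
|---|---|---|
| Labour odds ratio 3, 77% in labour, design rates | 91.4% | 91.4% |
| Same, pilot rates | 92.3% | 93.0% |
| Control PPH 3.8% and 7.8% by hospital | 91.1% | 91.1% |
| Control PPH 1.8% and 9.8% by hospital | 91.2% | 91.5% |
| Ten hospital-by-grade strata, 2.0% to 9.6% | 91.5% | 91.4% |

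Type I error was about 5% for both tests throughout (5.0% to 5.2% in the hospital and grade scenarios). In those scenarios the mean estimated risk difference was −3.7 points, the true value.

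**The case against.** The crude relative risk and risk difference are a legitimate primary analysis. Individual randomisation balances hospital and labour status in expectation, and the test's error rate already covers the chance imbalance that remains. The simulations bear this out, and that part of the objection stands in full.

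Several lesser points also stand. The difference in hospital mix rests on pre-COVID volumes; the April to August 2020 figures are 149 and 154 emergency sections a month, although they say nothing about elective cases. Labour status is already a prespecified subgroup, and risk factors for PPH are to be compared by arm, so a marked labour imbalance would probably be seen, though not adjusted for. With about 46 events, adjustment for hospital, labour and five operator grades together would be heavy, and by-hospital results (about 23 events each if equal) would be unstable. Hospital-specific lists may exist without being described.

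A reader might go further and infer that known operator and site differences distort the treatment comparison. The documents do not support this. They say only that experience may affect blood loss, and they give no PPH rate by grade or hospital.

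A reader might also infer that staff who know the arm would choose the operator accordingly. Nothing says when allocation is revealed or that the operator is chosen afterwards, and the Intervention section says all other management will be the same in both arms. The open-label design supports only a narrower point: since grade is not stated to be fixed before allocation, it should not be treated as a baseline covariate in the primary model.

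**Conclusion.** The point holds as a minor improvement to efficiency and prespecification. No stratification is stated, the main estimate is unadjusted although a factor the plan regards as strongly prognostic is available, no by-hospital result is planned, and operator grade has no stated use. The planned comparison is neither biased nor invalid.

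The size is small: a 95% chance shift of about ±0.2 points at the design control rate and about ±1.0 point at the pilot's, and a power change of about 0 to 0.7 points from stratified analysis. These figures assume a labour odds ratio of exactly 3 (the plan's lower bound), 77% in labour taken from the pre-COVID emergency share, and simple randomisation with equal arms. The case for change is that it costs very little, not that the trial is at risk without it.

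**What to change.** 1. In Randomization, state whether the list is stratified. Stratify by hospital and, where practicable, by caesarean in labour or not, as known at randomisation.
2. In Statistical methods and data reporting, prespecify the primary relative risk and risk difference adjusted for hospital and labour status, by Mantel-Haenszel or modified Poisson with robust errors. Report the crude result beside it.
3. Show the primary result by hospital, descriptively.
4. Tabulate operator grade by arm. Use it, with grades collapsed, only in a sensitivity analysis, because it may be determined after allocation.

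The cost is a few lines of analysis text and a stratified list; operator grade is already recorded, and hospital and labour status need only be available at randomisation. The downside is a slightly more complex analysis with about 46 expected events at the design rates, which is the reason to keep the adjustment to two binary factors.

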PPH contributes to near-miss cases in addition to actual deaths, due to the serious complications that can occur as a consequence of serious PPH. These include adult respiratory distress syndrome, coagulopathy, shock, loss of fertility, and pituitary necrosis (Sheehan syndrome) (4). If PPH is prevented this could contribute towards reduced hospital stay, avoidance of expensive interventions for intractable PPH (such as hysterectomies and the need for blood products) and conserve our already strained resources.

Prophylactic TXA use has been shown to produce a statistically significant decrease in postpartum blood loss; however, this may not convey clinical significance in terms of transfusion rates and maternal comorbidity from severe haemorrhage. Currently, there is no consensus regarding the optimal timing or dosing of prophylactic TXA for caesarean deliveries (33).

In the light of the above, this research proposes to assess the efficacy of TXA in preventing PPH after caesarean delivery in a population large enough to be adequately powered to add to the current body of evidence. Also, there are no published RCTs, in Southern Africa reporting on TXA in obstetric patients.

GOAL STATEMENT

The aim of this study is to compare the effect of a low dose of TXA (1 g) at the time of skin incision during caesarean delivery together with prophylactic oxytocin administration, versus prophylactic oxytocin alone in an open label randomized clinical trial.

RESEARCH QUESTION

Does intravenous TXA 1g plus Oxytocin 10 IU result in a lower incidence of primary postpartum haemorrhage compared to Oxytocin 10 IU alone after caesarean section?

OBJECTIVES

- 1. To assess the effect of TXA (1g) on postpartum blood loss at caesarean delivery.
- 2. To determine the potential adverse effects of intravenous TXA administered at caesarean section.

PRIMARY OUTCOME

Incidence of PPH, defined by a calculated estimated blood loss > 1000ml or a red blood cell transfusion up to day 2 postpartum

Secondary Outcomes

- Other outcome measures describing postpartum blood loss including
 - o calculated blood loss,
 - visually estimated blood loss,
 - o mean/median number of units of packed red blood cells transfused,
 - o incidence of postpartum shock;
 - o proportion of women requiring supplementary uterotonics,
 - o incidence of postpartum transfusion,
 - o incidence of emergency surgery for PPH including caesarean hysterectomies,

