Preoperative haematocrit will be determined on the day before elective caesarean or on the day of emergency caesarean delivery. Postoperative haematocrit will be the haematocrit obtained by blood sampling at D2 (on the second morning after caesarean section). If haematocrit is not available at D2, then haematocrit at D3 will be considered; if it is also missing, then the postpartum haematocrit closest to D2 in the absence of transfusion will be considered (36,37).

All women who receive RBC transfusion for PPH between delivery and D2 postpartum are defined to have PPH and meet the criteria for the primary outcome. Calculated blood loss is impossible to determine for these women. Moreover, women only rarely receive an RBC transfusion for a blood loss less than 1000 ml. As a marker of significant maternal morbidity, RBC transfusion is considered equivalent or superior to blood loss greater than 1000 mL(25).

Although visual estimation is the method used frequently by anaesthetists to estimate blood loss, it has been demonstrated as inaccurate in repeated studies. The estimate of blood loss is affected by amniotic fluid as well. Its continued use in clinical practice is likely related to tradition and it being easily used. We will also take note of the visual estimate made by the anaesthetist, and by the operating surgeon, as this is the method used locally(6,38)(39)

Secondary outcome measures

Describing postpartum blood loss

1. Clinical

- a. Visually estimated blood loss
- b. proportion of women requiring supplementary uterotonic treatment
- c. incidence of postpartum transfusion
- d. mean number of RBC units transfused
- e. incidence of emergency surgery for PPH including caesarean hysterectomies
- f. incidence of hypovolemic shock related to PPH as determined by assessing BP and pulse
- g. incidence of transfer to ICU
- h. incidence of maternal death from any cause
- i. length of hospital stay.

2. Laboratory

- a. incidence of calculated blood loss > 500 mL and > 1500 mL
- b. mean total calculated blood loss
- c. mean peripartum change in haemoglobin (difference between haemoglobin before delivery and at D2)
- d. Haemoglobin drop > 2 g/dL (between haemoglobin before delivery and at D2) (34).

Describing adverse events

1. Clinical

a. Hemodynamic parameters (heart rate, blood pressure) 15, 30, 45, 60, and 120 min after delivery

- b. the occurrence of potential mild adverse effects of TXA in the operating room:
 - i. nausea
 - ii. vomiting

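### One sentence in the primary outcome text conflicts with the haematocrit-based definition, and unmasked visual blood loss is a tested secondary outcome with no rule for which of two estimates is analysed

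*Combined protocol and SAP*

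**What the plan says.** **Primary outcome.** The section PRIMARY OUTCOME has PPH "defined by a calculated estimated blood loss > 1000ml", or a red-cell transfusion up to day 2. Under Assessment, Primary outcome measure, the text opens differently: "Estimated blood loss (EBL) will be determined using haematocrit, haemoglobin, and visual estimates". The formula that follows multiplies estimated blood volume (weight × 85) by the proportional fall in haematocrit. It has no haemoglobin term and no visual term. The same section justifies the calculation by the inaccuracy of other methods.

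**Visual estimate.** Later in that section the protocol calls visual estimation inaccurate and affected by amniotic fluid, then adds: "We will also take note of the visual estimate made by the anaesthetist, and by the operating surgeon". Secondary outcome measures lists "Visually estimated blood loss" as a clinical item. Statistical methods and data reporting gives quantitative outcomes a t-test or Wilcoxon rank-sum test and a mean difference with 95% CI. It puts secondary outcomes under Benjamini-Hochberg and repeats the secondary analyses in women delivered by caesarean during labour.

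**Masking.** Research design reads "Open-label parallel randomized control trial", and the Goal statement sets TXA plus oxytocin "versus prophylactic oxytocin alone in an open label randomized clinical trial". On who gives the drug, Intervention says "The participants in the intervention arm will receive generally from the anaesthetist or nurse anaesthetist TXA (1g"). No masked estimator is described.

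**The concern.** There are two separate issues.

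First, the primary measure is described in two ways. The definition and the formula point to haematocrit alone; the opening sentence names three sources and gives no role to two of them. The haematocrit rule runs from day 2 to day 3 to the closest value without transfusion, and says nothing about a woman with no postoperative value at all. The sentence should not be left available as grounds for a visual substitute once data are in hand.

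Second, visual loss is a judgement about the very quantity the drug is meant to reduce. It is made by theatre staff who, in an open-label trial with no placebo, can be expected to know the arm. Random inaccuracy only adds noise, but knowledge of the arm can push the estimates in one direction. The first objective is the effect of TXA on blood loss, so a significant visual result could be cited as support. With two estimates and no rule for choosing or combining them, the result can also depend on a choice made later.

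**Working it through.** **The primary text, side by side**

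- PRIMARY OUTCOME: calculated loss above 1000 mL, or transfusion.
- Formula: weight and haematocrit only.
- Opening sentence of Primary outcome measure: haematocrit, haemoglobin and visual estimates.
- Later in that section: visual estimates are noted in addition.
- Secondary outcome measures: haemoglobin change, haemoglobin drop and visual loss each appear as outcomes of their own.

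Four of the five places agree. Only the opening sentence conflicts, and no rule brings a visual estimate into the calculated loss.

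**The plan's sample size**

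Inputs from Sample size: 2.1% against 5.8%, "probability of a type I error (significance level) = 0.05" with Z = 1.96, 90% power, 1:1 allocation.

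- Pooled term: 1.96 × √(2 × 0.0395 × 0.9605) = 0.540
- Unpooled term: 1.28 × √(0.021 × 0.979 + 0.058 × 0.942) = 0.351
- n = (0.540 + 0.351)² / 0.037² ≈ 580 with these rounded normal quantiles, and 581 with exact quantiles

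The stated 581 per group reproduces, with power 90.0%.

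**How much shading makes the visual comparison significant**

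The SD of visual loss is not in the documents; 150 to 500 mL is assumed. No true drug effect is assumed, and means are compared by normal approximation.

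- SE = SD × √(2/581) = SD × 0.0587
- Shading that just reaches two-sided p = 0.05: 1.96 × SE
- Strictest Benjamini-Hochberg step: the plan gives no family size. Secondary outcome measures lists nine clinical and five laboratory blood-loss comparisons (counting the two calculated-loss cut-offs separately), so 14 is assumed. 0.05/14 = 0.0036, z ≈ 2.914, shading = 2.914 × SE
- Chance of p < 0.05 with shading d: Φ(d/SE − 1.96) + Φ(−d/SE − 1.96)

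| Assumed SD (mL) | SE (mL) | Shading for p = 0.05 (mL) | Shading at strictest step (mL) | Chance of p < 0.05, 25 mL | Chance of p < 0.05, 50 mL |
|---|---|---|---|---|---|
| 150 | 8.80 | 17.2 | 25.6 | 81% | about 100% |
| 200 | 11.73 | 23.0 | 34.2 | 57% | 99% |
| 250 | 14.67 | 28.7 | 42.7 | 40% | 93% |
| 300 | 17.60 | 34.5 | 51.3 | 30% | 81% |
| 400 | 23.47 | 46.0 | 68.4 | 19% | 57% |
| 500 | 29.34 | 57.5 | 85.5 | 14% | 40% |

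The nominal chance is 5%. For scale, one meta-analysis cited in the Literature review reports a mean reduction of 160.27 mL; every shading in the table is smaller.

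**Effect on the other secondary tests**

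Benjamini-Hochberg compares the k-th smallest p-value with k × 0.05/m. Without the visual test, the smallest of the other 13 must meet 0.05/13 = 0.0038. If a visual p-value driven by shading ranks first among 14, that same outcome ranks second and is compared with 2 × 0.05/14 = 0.0071.

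**The case against.** **The primary is safe as defined.** A reader might infer from the opening sentence that unmasked visual estimates enter the primary endpoint and bias it. The documents do not support that. The definition specifies calculated loss, the formula that follows defines that term from weight and haematocrit, and the visual estimate is then noted in addition and listed as secondary. The sentence is most naturally a loose list of the measurements collected. This objection stands in full: for the primary there is wording to reconcile and nothing more.

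**The multiplicity rule raises the bar.** Unadjusted p-values overstate how easily visual loss would be declared significant. Take 50 mL of shading and an SD of 300 mL: z = 50/17.60 = 2.84, p = 0.0045, which just misses 0.0036. The chance of passing the strictest step with 50 mL is about 91%, 47% and 22% at SDs of 200, 300 and 400 mL. This stands, and it is why the adjusted shading is shown above. But Benjamini-Hochberg addresses chance findings. It does not remove a systematic shift, and its threshold loosens when other outcomes are significant.

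**Injector and estimator need not be the same person.** The drug may be given by a nurse anaesthetist, and knowledge of the arm is inferred from the open-label design. This is fair. The point needs only that estimators are not masked, and no masking is described.

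**It is one weak secondary outcome, and the protocol says so.** True, which limits the severity. The protocol's caveat, however, concerns accuracy, not knowledge of the arm.

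**Conclusion.** The point holds in two limited parts, and its severity is minor.

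1. One sentence under Primary outcome measure conflicts with the primary definition and formula. It must be reconciled; no bias in the primary is shown.
2. Visual loss is an unmasked, subjective outcome in the tested secondary family, with no rule for which of two estimates is analysed. With no drug effect, mean shading of about 17 to 57 mL suffices for p = 0.05, or about 26 to 85 mL at the strictest Benjamini-Hochberg step.

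These sizes rest on an assumed SD of 150 to 500 mL and an assumed family of 14 tests. The documents give no evidence that shading of any particular amount will occur. A reader might go further and infer that a significant trial result could come from shading alone. That does not follow: the arithmetic concerns the visual secondary comparison only.

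**What to change.** - Under Primary outcome measure, replace the opening sentence with a statement that blood loss for the primary outcome comes from the haematocrit formula only, with transfusion as in PRIMARY OUTCOME. Leave haemoglobin and visual estimates to the secondary list.
- Report the anaesthetist's and the surgeon's estimates separately, by arm, as unmasked descriptive data without a p-value and outside the Benjamini-Hochberg family.
- Use mean total calculated blood loss, already a laboratory secondary outcome, as the tested continuous measure.

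If the team prefers to keep a visual comparison, a masked estimator would also answer the concern. Retaining the present comparison with a clear unmasked label would be a weaker alternative, and it would still need a prespecified choice of estimate.

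The cost is wording and one secondary test given up. The primary stays at 581 per arm with 90.0% power.
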